7.3 Exclusion Criteria

Patients who have met any of the following criteria will be excluded from the study:

- Diagnosis of Type 1 diabetes
- T2DM on treatment with DPP-IV or insulin currently

- Treatment with GLP-1 receptor agonists within the last 6 months and/or have a history of GLP-1 receptor agonist intolerance
- Treatment with anti-obesity drugs within 12 weeks prior to randomisation
- eGFR $\leq 30\text{ml}/\text{min}/1.73\text{m}^2$ on serum testing over the last 26 weeks
- Females referred to the clinic because of fertility problem
- Females of child bearing potential who are pregnant, breast-feeding or intend to become pregnant or are not using or willing to use adequate contraceptive methods (as described in Section 8.3.1)
- Have terminal illness
- Are not primarily responsible for their own care
- Any other significant disease or disorder which in the opinion of the investigator, may either put the participants at risk or may influence the result of the study or the participant's ability to participate
- Untreated or uncontrolled hypothyroidism/hyperthyroidism defined as thyroid-stimulating hormone, as defined by local sites pathology laboratory reference ranges as outside the normal range; mIU/litre (see local site laboratory reference ranges)
- Family or personal history of multiple endocrine neoplasia type 2 (MEN2) or familial medullary thyroid carcinoma (FMTC)
- Personal history of non-familial medullary thyroid carcinoma
- History of chronic pancreatitis or idiopathic acute pancreatitis
- Amylase levels three times higher than the upper normal range
- Obesity induced by other endocrinologic disorders (e.g. Cushing's Syndrome)
- Current or history of treatment with medications that may cause significant weight gain, within 12 weeks prior to randomisation, including systemic corticosteroids (except for a short course of treatment, i.e. 7–10 days), atypical antipsychotic and mood stabilizers (e.g. clozapine, olanzapine, valproic acid and its derivatives, and lithium)
- Initiation of antidepressants during the last 12 weeks
- Previous surgical treatment for obesity <1 year before trial entry weight loss procedures/surgery including removal of a gastric band and/or gastric balloon
- History of other severe psychiatric disorders
- History of known or suspected abuse of alcohol and/or narcotics
- History of major depressive episode during the last 2 years

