8.3.1.1 Randomisation

Randomisation will be conducted through a validated online system (sealedenvelope.com) provided through the LCTU. Eligible participants will be randomly assigned at their Baseline Visit (Day 0) in a 2:1 ratio to participate in a Tier 3 service with:

- 1) Targeted prescribing pathway - The use of once daily subcutaneous injections of Liraglutide (if they meet the pre-specified criteria), starting at a dose of 0.6 mg with gradual and pre-specified increments to 3.0mg
or
- 2) Control Group - No additional treatment.

A 2:1 ratio will be used so that a sufficient number of responders will be available for responder analyses (see Section 11). Randomisation will be stratified by centre and BMI ($\geq 45\text{kg}/\text{m}^2$; $< 45\text{kg}/\text{m}^2$). Participants will be informed of their randomisation assignment during the Baseline Visit. A letter will be sent to the participant's GP notifying them of their patient's participation in the study. Both the participant and their GP will have the randomisation assignment confirmed by letter.

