8.3.1.2 Titration Protocol

During the baseline visit, participants randomised to the targeted prescribing pathway group will be offered LIRA 3mg for the next 16 weeks and will be re-informed of the potential side effects of the medication. The research team will explain to participants in this group the titration protocol and the weight loss targets in order to continue receiving treatment with LIRA 3mg. All participants who will start on LIRA 3mg will be trained to self-administer the treatment injection once daily. Dose escalation of Liraglutide will occur according to a pre-specified titration protocol, from 0.6mg to a maximum of 3.0mg. Participants in the targeted prescribing pathway will continue to be prescribed LIRA 3mg for the duration of the study unless they do not meet the pre-defined weight loss targets

at each stopping point (after 16, 32 and 52 weeks – see Section 6.2 for stopping rules). Participants will be withdrawn from receiving LIRA 3mg if the doses are not tolerated during or following the titration period. Liraglutide dose will be initiated at 0.6mg and then steadily increased by the doses below. The up titration to maximum dose must be achieved by week 8.

- 0.6mg
- 1.2mg
- 1.8mg
- 2.4mg
- 3.0mg.

Participants in the Targeted Prescribing Pathway will undergo titration reviews fortnightly during weeks 0-8. During these visits, there will be the option for telephone calls between weeks 1-3 and weeks 3-5 available to research team and for participants to counsel them on titration requirements. The titration protocol will be explained to the participants during the baseline visit and reviewed by the clinician at weeks 3, 5 and 8.

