Secondary outcomes measured at 52 weeks and 104 weeks will be analysed in a similar way, with binary outcomes compared using logistic regression models and summarised using proportion (95% confidence interval), and continuous outcomes compared using linear regression models and summarised using mean (95% confidence interval). If continuous outcomes are non-normally distributed then they will be transformed or a more suitable regression model will be selected. In all analyses, participants will be analysed in the group to which they were randomised at baseline. Only the complete cases population will be used for the secondary outcomes to reduce the number of models being fitted. Participants who have undergone bariatric surgery during the period of the study will be excluded from these analyses. Data on treatment adherence, safety (including adverse events), and treatment satisfaction will be summarised and tabulated.

As additional secondary analyses, we will perform a responder analysis which will repeat the analyses of the secondary outcomes with the intervention group restricted to those participants who responded to the targeted prescribing pathway (i.e. had achieved $\geq 15\%$ weight loss at 52 weeks after randomisation). The purpose of these analyses is to compare the outcomes of “early and good” responders to the targeted prescribing pathway with those who received standard care only. Therefore, all participants randomised to the standard care group will also be included in these responder analyses.

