Adherence with other anti-obesity medications [#]								X		X	X				X
Adherence to Tier 3 (or equivalent) Service			X	X	X	X	X	X	X	X	X	X	X	X	X
Contacts with GP/HCP		X	X	X	X	X	X	X	X	X	X	X	X	X	X
Inpatient and Outpatient apt's		X	X	X	X	X	X	X	X	X	X	X	X	X	X
Medications cost		X									X				X
QUESTIONNAIRES^{^^^}															
HSRUQ		X									X				X
TSQM###		X									X				X
EQ-5D		X									X				X
IWQOL-Lite		X									X				X
IPAQ-Long		X									X				X
PHQ-9		X									X				X

*Only for participants at the LIRA 3mg group who are on active treatment

^{§§}Target dose by week 8. ^{§§}Optional Telephone calls to check tolerance and up-titrate at weeks 1, 3 & 5.

**As required for participants with identified risk OSA or current OSA based on CPAP use and type of CPAP (variable or fixed pressures CPAP)

*** Only for prediabetic, diabetic and hypertensive individuals

****Where possible the week 52 visit should continue to be scheduled within the (± 14 days) study visit window, however to aid retention

and to help maximise data collection for the study primary end point, the week 52 visit window can be extended to ± 3 months.

Only for participants in the standard care group on treatment with anti-obesity drugs

#[#] Only for participants with diagnosis of T2DM

#^{##} For participants on treatment either with LIRA 3mg or other anti-obesity medication

[^] Only participants who report problems with injection and/or side-effects may be reviewed by study clinician

^{^^} A repeat screening visit may take place to assess eligibility

Drug dispensing unscheduled visits may occur at any point within the study period for participants in LIRA3 mg group as required (not depicted above)

^{^^^}In response to the COVID19 global pandemic, an interim time point for the quality of life questionnaires has been added (HSRUQ, TSQM, EQ-5D, IWQOL-Lite, IPAQ-Long and PHQ-9). These will be sent out to all participants during the COVID19 pandemic.

^{^^^^} These activities will not be completed during the COVID19 pandemic restriction period, however once restrictions are lifted participants that resume face to face visits will be completed as per the original protocol.

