Proportion of those with diabetes at baseline with HbA1C<6.5%	52, 104	From HbA1c measurement, a binary indicator will be derived, being 1 if participant achieves the target and 0 if they do not.
Change in Albumin-Creatinine Ratio (ACR; mg/mmol) from baseline for participants with diabetes, prediabetes, or hypertension	52, 104	Follow-up ACR – baseline ACR, only for participants defined as having diabetes, prediabetes, or hypertension
Obesity-related co-morbidities and their treatments (Hypertension)		

Systolic blood pressure (mmHg)^b	52, 104	Follow-up systolic blood pressure – baseline systolic blood pressure
Diastolic blood pressure (mmHg)^b	52, 104	Follow-up diastolic blood pressure – baseline diastolic blood pressure
Hypertension	52, 104	Binary indicator of 1 if participant is on antihypertensive medications or systolic blood pressure > 140 mmHg ^c , 0 otherwise with baseline values also presented
Number of agents for hypertension	52, 104	Change from baseline in total number of medications taken for hypertension defined as medications in any of the following classes: ACE-inhibitors, calcium channel blockers, thiazide diuretics, alpha-blockers, and beta-blockers.
Obesity-related co-morbidities and their treatments (Dyslipidaemia)		
LDL cholesterol (mmol/L)	52, 104	Follow-up LDL cholesterol – baseline LDL cholesterol
HDL cholesterol (mmol/L)	52, 104	Follow-up HDL cholesterol – baseline HDL cholesterol
Total cholesterol (mmol/L)	52, 104	Follow-up total cholesterol – baseline total cholesterol
Triglycerides (mmol/L)	52, 104	Follow-up triglycerides – baseline triglycerides
Number of agents for dyslipidaemia	52, 104	Change from baseline in total number of medications taken for dyslipidaemia defined as medications in any of the following classes: statins, fibrates, and ezetimibe.
Number of participants referred for other obesity intervention		
Referred to Tier 4 for bariatric surgery	104	Binary indicator of 1 if participant was referred to Tier 4 for bariatric surgery over 104 week period, 0 otherwise
Treatment satisfaction		
Treatment	Satisfaction	Questionnaire for Medication (TSQM)
	52, 104	Change from baseline in TSQM scale score. Scored as per version II (detailed in Appendix B on vhe.066.fm (iqvia.com)).
Safety/adverse events		
Gastrointestinal symptoms	52, 104	Binary indicator of 1 if participant experienced any nausea or vomiting in study up until the time point of interest (captured in the expected AEs), 0 otherwise

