5.8 Changes to the Planned Analysis

In the protocol, it stated that most secondary outcomes would be subject to formal statistical testing, with some secondary outcomes (safety, treatment compliance, treatment satisfaction) tabulated only, without statistical testing. However, due to the large number of secondary outcomes, it was decided that more secondary outcomes should be tabulated only to reduce the impact of multiple testing. The following outcomes were the ones for which the approach changed: obesity-related comorbidities, referrals to Tier 4 services, and physical activity.

In the protocol, the majority of the secondary outcomes were listed as absolute values, however the change from baseline will instead be analysed for continuous variables.

In the protocol, it states that ACR will be analysed as a secondary outcome for participants with diabetes. However, ACR was also measured for participants with prediabetes or hypertension and so these have been added to the ACR secondary outcome definition.

In the protocol, it was stated that participants who had bariatric surgery would be excluded from the complete cases, per protocol, and responder populations. However, it is more likely that these individuals will be poor responders and so excluding them could potentially bias the analyses. Therefore, participants who had bariatric surgery during the study period will be only be included at time-points prior to their bariatric surgery. They will be excluded from time-points after their bariatric surgery.

In the protocol, it stated that adjusted proportions or means would be presented by treatment group in the primary and secondary analyses. However, the unadjusted raw values are presented instead.

6 Safety and Adverse events (AEs)

The safety outcomes (including AEs and SAEs) will be summarised overall, by randomisation group, and by whether or not the participant was currently receiving LIRA 3mg treatment using count and percentage. The following information will also be presented:

- Incidence rate (per person-year) of each System Organ Class of AEs by treatment and overall
- Proportion of participants with at least one AE, by System Organ Class type, treatment arm, and overall
- Incidence rate (per person-year) of each expected AE type by treatment and overall
- Proportion of participants with at least one expected AE, by AE type, treatment arm, and overall
- Bar chart of number of AEs per individual, split by treatment

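### The TSQM endpoint is defined as change from baseline, but by design no participant has a relevant medicine to rate at baseline, so the change score cannot be interpreted

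*SAP*

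**What the plan says.** SAP Section 2.2.1 gives one treatment-satisfaction endpoint, the Treatment Satisfaction Questionnaire for Medication (TSQM) at weeks 52 and 104, derived as "Change from baseline in TSQM scale score". The Table 16.11 template gives TSQM baseline, follow-up and change columns for both arms.

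The protocol does not ask for a change score. Section 11.1 says "Data on treatment adherence, safety (including adverse events), and treatment satisfaction will be summarised and tabulated". The change score appears to come from SAP Section 5.8, which says of most secondary outcomes that "the change from baseline will instead be analysed for continuous variables". No exception is made there for TSQM.

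The TSQM row of the schedule in Protocol Appendix 3 is marked at week 0, week 52 and week 104. It carries a footnote limiting who completes it: "For participants on treatment either with LIRA 3mg or other anti-obesity medication".

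**The concern.** A medication-satisfaction score needs a medication that the respondent has used. The footnote accepts this by tying TSQM to people on treatment. The trial is designed so that participants enter off anti-obesity treatment and, in the intervention arm, start LIRA on the day of the baseline visit. A week-0 score therefore cannot express satisfaction with LIRA or with another current anti-obesity drug, and the difference between it and a later score does not measure treatment satisfaction.

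Patient satisfaction is secondary objective 9 in both documents, and TSQM is the only measure listed for it. If the derivation is followed literally, the number reported for that objective either cannot be calculated for most people or contrasts satisfaction with two different medicines.

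**Working it through.** The documents give no count of baseline TSQM forms, so there is no planned figure to reproduce. The check sets the provisions side by side.

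1. **Who completes TSQM.** Participants taking LIRA 3mg or another anti-obesity drug (Protocol Appendix 3, footnote to the TSQM row).
2. **Other anti-obesity drugs before baseline.** Protocol Section 7.3 excludes "Treatment with anti-obesity drugs within 12 weeks prior to randomisation".
3. **LIRA's drug class before baseline.** The same section excludes "Treatment with GLP-1 receptor agonists within the last 6 months".
4. **Timing of allocation.** Protocol Section 8.3.1.1: "Eligible participants will be randomly assigned at their Baseline Visit (Day 0) in a 2:1 ratio".
5. **Start of LIRA.** Protocol Section 8.3.1.2: "During the baseline visit, participants randomised to the targeted prescribing pathway group will be offered LIRA 3mg for the next 16 weeks". There is no earlier exposure to rate.

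From 2 and 3, an eligible person arrives at week 0 on none of the medicines named in 1. From 4 and 5, LIRA becomes available only at that visit, after allocation. Participants with a valid on-treatment baseline, by design:

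- intervention: 0 of 261
- standard care: 0 of 131
- total: 0 of 261 + 131 = 392

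So by design no valid change score exists in either arm. A form completed on day 0 would rate LIRA before any experience of it, an anti-obesity drug stopped more than 12 weeks earlier, or an unrelated medicine. None of these is a baseline for the follow-up score.

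**Who contributes at follow-up.** The stopping rules (Protocol Section 6.2) also shape the week 52 and 104 scores. To be on LIRA at the week-52 visit, a participant must have lost at least 5% at week 16 and at least 10% at week 32. To continue to week 104, the participant must also have lost at least 15% at week 52. The sample-size section expects 16% of the intervention arm to reach 15%:

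- 0.16 × 261 = 41.8, which the plan gives as an estimated 40
- 40 / 261 = 15.3%
- with the plan's 25% drop-out applied: 0.16 × 261 × 0.75 = 31.3

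About 40 is therefore a generous estimate of LIRA users at week 104, because some of those who reach 15% will already have stopped the drug. The SAP's TSQM row states no on-treatment restriction, whereas the neighbouring LIRA adherence endpoints do limit their denominators.

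**The case against.** The strongest reply is that the SAP already allows for this. Section 5.5.1 lists treatment satisfaction among the descriptive outcomes. It says that baseline, follow-up and change are summarised where that is sensible, and that outcomes definable only at follow-up are exempt. Table 16.11 has follow-up columns for TSQM. A reader might infer from the endpoint definition that the analysis has no valid data, or that the result will be empty. The documents do not support that: observed week 52 and 104 scores are valid and would be tabulated. This part of the objection stands. It does not rescue the endpoint itself, because the general exemption names no outcome, while Section 2.2.1 and the table template explicitly give TSQM a change from baseline.

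Second, the schedule marks TSQM at week 0 and LIRA is dispensed that day, so some intervention participants might be counted as on treatment and complete the form. That is possible, and it means that the baseline fields need not be empty. The week-0 mark nevertheless conflicts with its own footnote, and a form completed on the day of first dispensing cannot reflect use of the drug.

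Third, the restriction was not applied uniformly: during the pandemic the TSQM was sent to all participants at an interim time point. That is true, but an interim form supplies no baseline. Even if the footnote were read as not applying to TSQM, a week-0 score would concern some other medicine, and the change would still compare different drugs.

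Finally, the consequence is small. No test or model is planned for TSQM. That is accepted.

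**Conclusion.** The derivation is wrong as written, for one descriptive secondary outcome. By design, 0 of 392 participants have a valid TSQM baseline, so the change score cannot be interpreted in either arm. The follow-up scores remain usable. The primary analysis, power, alpha and safety reporting are not affected.

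The conclusion assumes that the eligibility criteria are met and that the schedule footnote applies to the TSQM row on which its marker appears. The zero is inferred from the design and is not a count of forms received; some week-0 forms may exist.

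A second tempting inference is that the follow-up scores compare the arms on satisfaction. They do not. They come from people still on a drug, selected after randomisation by weight loss, tolerance or local prescribing. At week 104 the LIRA scores describe responders still on treatment.

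**What to change.** 1. In SAP Section 2.2.1, replace the change from baseline with the observed TSQM scale score(s) at weeks 52 and 104 among participants on LIRA 3mg or another anti-obesity drug at that time. Say whether being on treatment at week 52 is judged before or after the week-52 stopping rule is applied.
2. Present the scores by arm and by drug, showing the number on treatment and the number with a completed form.
3. In Table 16.11, remove the TSQM baseline and change columns. In Section 5.5.1, name TSQM as a follow-up-only outcome, and list it in Section 5.8 as an exception to the move to change scores.
4. Add a sentence saying that, under the stopping rules, week-104 LIRA users are those who had lost at least 15% at week 52 (about 40 of 261 on the plan's figure), so the scores describe satisfaction among responders still on treatment and are not a randomised comparison.
5. Note that the week-0 mark and the footnote in Protocol Appendix 3 conflict, and that any week-0 forms will not be used as a baseline.

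The cost is SAP wording and one table shell. The follow-up forms are already scheduled. The supplied SAP is marked as a draft and is to be finalised before database lock, so the change can be made in that revision.

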14.10 Other Ethical Considerations

14.10.1 Known and potential risks

LIRA 3mg is administered as a one daily subcutaneous injection and is available in a prefilled, disposable pen device comprising a pen injector and cartridge. There may be some anxiety and concern to starting treatment using a needle-based device and this will be discussed at length with their clinician. It can be taken at any time of the day and is meal independent. The pros and cons of LIRA 3mg will be explained to each participant during the initial consultation for study consent.

LIRA 3mg has a good tolerability profile; however the most frequently reported adverse effects of LIRA 3mg are gastrointestinal, including nausea, diarrhoea, vomiting, constipation, abdominal pain, and dyspepsia. These gastrointestinal adverse effects may occur more frequently at the start of treatment with LIRA 3mg, and usually diminish within a few days or weeks on continued treatment. Hypoglycaemia is considered low risk with this treatment because its action is glucose dependent. However, participants suffering with diabetes on treatment with sulphonylureas may be at higher risk for hypoglycaemic episodes compared to the other participants.

Rare serious adverse events may include hepatobiliary diseases such as associated with gallstone formation and pancreatitis. An increase incidence of breast malignancies previously reported may be due to reduced adipose tissue in the breast and earlier detection.

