Overall hypoglycaemia rate – ADA definition	52, 104	Hypoglycaemia events will be defined as per Appendix 5 for people without

		diabetes and as per the ADA definition in Appendix 5 for people with diabetes. Hypoglycaemia rate will be calculated per participant as total number of hypoglycaemia events divided by the total follow-up time.
Overall hypoglycaemia rate – Novo Nordisk	52, 104	Hypoglycaemia events will be defined as per Appendix 5 for people without diabetes and as per the Novo Nordisk definition in Appendix 5 for people with diabetes. Hypoglycaemia rate will be calculated per participant as total number of hypoglycaemia events divided by the total follow-up time.
AEs	Continual	Defined as in protocol with MEDRA coding used to classify AEs into System Organ Classes
SAEs	52, 104	Defined as in protocol with MEDRA coding used to classify SAEs into System Organ Classes
Rates of severe hypoglycaemia	52, 104	Calculated per participant as total number of severe hypoglycaemia events divided by the total follow-up time, where severe hypoglycaemia is defined as hypoglycaemic episodes requiring the assistance of another person to actively administer carbohydrate, glucagon, or other resuscitative actions (i.e., 'severe hypoglycaemic episodes')
Change in heart rate from baseline (beats per minute)	52, 104	Follow-up heart rate – baseline heart rate
Compliance of patient with the treatment		
Compliant with Tier 3 service (completers)	52, 104	Binary indicator of 1 if participant is compliant, 0 otherwise (defined in study database)
Stopped treatment with LIRA 3mg because of adverse effects	52, 104	Binary indicator of 1 if participant stopped treatment with LIRA 3mg because of adverse effects*, 0 otherwise. Only defined for participants in intervention arm who were currently eligible for LIRA 3mg treatment. * This includes main reason of 'adverse event' or 'unable to tolerate drug'.
The adherence of participants with the LIRA	52, 104	Participants will be defined as treatment compliant if they self-administer at least 70% of planned doses. Binary indicator of 1 if participant is compliant, 0 otherwise.

3mg (monitored through specific questionnaire and return of used pens)		Given the change in visits as a result of COVID-19 to allow face-to-face, this will be defined using the questionnaire answers as detailed in Appendix 7. Only defined for participants in intervention arm who were currently eligible for LIRA 3mg treatment.

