16.13 Summary of continuous safety outcomes

Outcome	Baseline		Follow-up		Change from baseline	
	Control	Intervention	Control	Intervention	Control	Intervention
Overall hypoglycaemia rate – ADA definition at 52 weeks						
Number						
Mean						
SD						
Median						
Range						
Interquartile range						
Overall hypoglycaemia rate – ADA definition at 104 weeks						
Number						
Mean						
SD						
Median						
Range						
Interquartile range						
Overall hypoglycaemia rate – Novo Nordisk definition at 52 weeks						
Number						
Mean						
SD						
Median						
Range						
Interquartile range						
Overall hypoglycaemia rate – Novo Nordisk definition at 104 weeks						
Number						
Mean						
SD						
Median						
Range						
Interquartile range						
Overall adverse event rate at 52 weeks						
Number						
Mean						
SD						
Median						
Range						
Interquartile range						

Outcome	Baseline		Follow-up		Change from baseline	
	Control	Intervention	Control	Intervention	Control	Intervention
Overall adverse event rate at 104 weeks						
Number						
Mean						
SD						
Median						
Range						
Interquartile range						
Overall serious adverse event rate at 52 weeks						
Number						
Mean						
SD						
Median						
Range						
Interquartile range						
Overall serious adverse event rate at 104 weeks						
Number						
Mean						
SD						
Median						
Range						
Interquartile range						
Overall severe hypoglycaemia event rate at 52 weeks						
Number						
Mean						
SD						
Median						
Range						
Interquartile range						
Overall severe hypoglycaemia event rate at 104 weeks						
Number						
Mean						
SD						
Median						
Range						
Interquartile range						
Heart rate (beats per minute) at 52 weeks						
Number						

Outcome	Baseline		Follow-up		Change from baseline	
	Control	Intervention	Control	Intervention	Control	Intervention
Mean						
SD						
Median						
Range						
Interquartile range						
Heart rate (beats per minute) at 104 weeks						
Number						
Mean						
SD						
Median						
Range						
Interquartile range						

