16.15 Summary of Adverse events by MEDRA and expected adverse event terms

Incidence rate (per person year) of each System Organ Class of AEs by treatment and Overall

System Organ Class	Standard		Liraglutide		Overall		
	N	Incidence	N	Incidence	N	Incidence	Incidence Rate Ratio
Blood and lymphatic system disorders							
Cardiac disorders							
Congenital, familial and genetic disorders							
Ear and labyrinth disorders							
Endocrine disorders							
....							

Proportion of patients with at least one AE, by SOC type, treatment arm and overall

System Organ Class	Standard		Liraglutide		Overall	
	N	%	N	%	N	%
Blood and lymphatic system disorders						
Cardiac disorders						
Congenital, familial and genetic disorders						
Ear and labyrinth disorders						
Endocrine disorders						
....						

Incidence rate (per person year) of each Expected AE Type by treatment and Overall

Expected AE Type	Standard		Liraglutide		Overall		
	N	Incidence	N	Incidence	N	Incidence	Incidence Rate Ratio
N/A							
Anaphylactic reaction							
Hypoglycaemia							
Dehydration							
Dizziness							
Nausea							
.....							

Proportion of patients with at least one expected AE, by AE type, treatment arm and overall

Expected AE Type	Standard		Liraglutide		Overall	
	N	%	N	%	N	%
N/A						
Anaphylactic reaction						
Hypoglycaemia						
Dehydration						
Dizziness						
Nausea						
.....						

Proportion of individuals with at least one AE of given Severity by treatment and overall

Severity	Standard		Liraglutide		Overall	
	N	%	N	%	N	%
Mild						
Moderate						
Severe						
Fatal						

Proportion of individuals with at least one AE of given Likelihood Related by treatment and overall

Likelihood Related	Standard		Liraglutide		Overall	
	N	%	N	%	N	%
Not Related						
Unlikely						
Possible						
Probable						
Definite						

Incidence rate (per person year) of each System Organ Class of SAEs by treatment and Overall Incidence Rate						
System Organ Class	Standard N	Incidence	Liraglutide N	Incidence	Overall N	Incidence Rate Ratio
Blood and lymphatic system disorders						
Cardiac disorders						
Congenital, familial and genetic disorders						
Ear and labyrinth disorders						
Endocrine disorders						
...						

Proportion of patients with at least one SAE, by SOC type, treatment arm and overall

System Organ Class	Standard		Liraglutide		Overall	
	N	%	N	%	N	%
Blood and lymphatic system disorders						
Cardiac disorders						

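### Table 16.13 averages safety rates participant by participant, so short follow-up gets too much weight; events per person-year by arm should replace this

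*SAP*

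**What the plan says.** SAP 2.2.1 (Safety/adverse events) lists the overall hypoglycaemia rate twice, under the ADA and the Novo Nordisk definitions. Both rows carry the same derivation: "Hypoglycaemia rate will be calculated per participant as total number of hypoglycaemia events divided by the total follow-up time". The severe hypoglycaemia row reads: "Calculated per participant as total number of severe hypoglycaemia events divided by the total follow-up time". Total follow-up time is not defined.

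The AE row of the same table has no rate formula, only "Defined as in protocol with MEDRA coding used to classify AEs into System Organ Classes", and the SAE row is worded in the same way. Even so, the shell in SAP 16.13 (continuous safety outcomes) has rows such as "Overall adverse event rate at 52 weeks" beside the hypoglycaemia rows. Each row asks for number, mean, SD, median, range and interquartile range by arm, with Baseline, Follow-up and Change columns.

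Elsewhere the SAP uses person-time. Section 6 asks for "Incidence rate (per person-year) of each System Organ Class of AEs by treatment and overall" and "Proportion of participants with at least one AE, by System Organ Class type, treatment arm, and overall". Table 16.15 has "Incidence rate (per person year) of each Expected AE Type by treatment and Overall", with Hypoglycaemia and Nausea among its rows and an incidence rate ratio column. It repeats this for SAEs.

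**The concern.** A mean of individual rates weights people, not time at risk. Someone who leaves after a few weeks with one event has a very high personal rate, and that rate enters the arm mean with the same weight as one based on full follow-up. The mean then depends heavily on who left early. It can also move away from events per person-year if risk changes over time. Protocol 14.10.1 gives one reason to expect that: gastrointestinal effects "may occur more frequently at the start of treatment with LIRA 3mg".

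The outcomes affected are the overall AE, overall SAE, ADA, Novo Nordisk and severe hypoglycaemia rates. These are safety outcomes named in Protocol 6.4.2, and no person-time version of them is planned. Hypoglycaemia would also be reported on two scales, in Tables 16.13 and 16.15. The two could differ through weighting alone, on top of any difference in event definition.

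**Working it through.** **Inputs from the documents.** Arms of 261 and 131, and 25% drop-out (Protocol 11.2, SAP 1.2.4). These come from a sample-size statement that reproduces closely: 96 + 192 = 288 evaluable, and 288/0.75 = 384, against 392 stated (2.0% apart). The documents give no AE or hypoglycaemia rate and no timing for drop-out, so there is no planned safety figure to reproduce. Event rates and leaving times below are assumptions.

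**1. Weight of one event (no event rate needed).** Take *n* participants, *P* person-years in the arm, and one event in a participant followed for *t* years. It adds 1/(*n t*) to the mean of individual rates and 1/*P* to the pooled rate.
- Follow-up of 4 weeks: own rate 52/4 = 13 per year, so the mean rises by 13/261 = 0.050.
- Pooled, with *P* = 230 assumed: 1/230 = 0.0043, a ratio of 11.5. If instead 196 stay the full year and 65 leave at week 4, *P* = 196 + 65 × 4/52 = 201 and 1/201 = 0.0050, a ratio of 10.
- Exit at week 2: 26/261 = 0.100 against about 0.005, a ratio of about 20. Exit at week 16: 3.25/261 = 0.012 against 0.005.

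**2. Median.** If fewer than half the arm has any event, the median individual rate is 0 whatever the others have. At an assumed 0.2 events per year, the simulated median was 0.00.

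**3. Mean of rates against pooled rate.** Simulation over 52 weeks, 4,000 runs per scenario, base rate 2 events per year, 25% leaving unless stated, *n* = 261 unless stated. Early risk means weeks 0 to 8.

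| Scenario (assumed) | Mean of rates | Pooled | Ratio |
|---|---|---|---|
| Constant risk, leaving weeks 1–16 | 2.001 | 1.999 | 1.00 |
| Early risk ×3, nobody leaves | 2.616 | 2.616 | 1.00 |
| Early risk ×3, leaving weeks 1–52 | 2.888 | 2.689 | 1.07 |
| Early risk ×3, 10% leaving weeks 1–16 | 2.889 | 2.660 | 1.09 |
| Early risk ×3, leaving weeks 1–16 | 3.303 | 2.738 | 1.21 |
| Early risk ×5, leaving weeks 1–16 | 4.601 | 3.483 | 1.32 |
| Early risk ×0.33, leaving weeks 1–16 | 1.568 | 1.753 | 0.89 |
| Early risk ×3, each leaver has one extra event, leaving weeks 1–16 | 5.690 | 3.055 | 1.86 |
| Control, *n* = 131, constant risk, same leaving rule | 4.405 | 2.320 | 1.90 |

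Hand check of the fifth row, with leaving time *T* uniform on weeks 1–16:
- Stayers' rate: 2 × (3 × 8 + 44)/52 = 2.615.
- Leavers' mean own rate: 2 + 4 × E[min(1, 8/*T*)] = 2 + 4 × (7 + 8 ln 2)/15 = 5.345.
- Mean of rates: 0.75 × 2.615 + 0.25 × 5.345 = 3.30.
- Pooled events per participant: E[*T*] = 8.5 and E[min(*T*, 8)] = 6.367, so 0.75 × 2.615 + 0.25 × (2/52)(8.5 + 2 × 6.367) = 2.166.
- Pooled person-years per participant: 0.75 + 0.25 × 8.5/52 = 0.791. The pooled rate is 2.166/0.791 = 2.74.

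**4. Precision without bias.** Under constant risk with leaving in weeks 1–16, the SD of the arm rate is 0.158 for the mean of rates and 0.099 pooled. With leaving spread over weeks 1–52 it is 0.116 against 0.093.

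**The case against.** The case against making much of this is substantial.

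- **Person-time rates are already planned.** Section 6 and Table 16.15 give incidence per person-year by class and by expected type, with rate ratios and proportions with at least one event. Early nausea, and hypoglycaemia recorded as an expected AE, are therefore covered. This stands; the gap is limited to the five rates named above.
- **The explicit formula and the early-risk statement concern different outcomes.** The per-participant wording covers hypoglycaemia only, which Protocol 14.10.1 calls low risk with no early timing. Early timing is stated only for gastrointestinal effects, whose own endpoint in SAP 2.2.1 is a yes/no indicator. This stands: the directional argument bears on the overall AE rate, where the per-participant calculation is inferred from the table shell.
- **The tables are descriptive.** Safety is not tested, and Table 16.13 contains no between-arm contrast. This stands and limits the consequence. The median shown beside the mean is no safeguard for rare events (step 2).
- **Stopping LIRA does not end observation** (Protocol 8.8.4); leaving the study does (8.8.1). This also stands. However, SAP Appendix 7 provides for people recorded as not completing the trial because they stopped LIRA, and Protocol 9.2 anticipates drop-out from side effects. Some early exit is foreseen, though not quantified.

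A reader might infer that the intervention arm's rate will be inflated and the comparison with standard care wrong. The documents do not support that. They give no event rates or leaving times, and the direction reverses if early risk is lower. Control is inflated about as much (1.90 against 1.86) if its leavers also go after an event.

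**Conclusion.** The point holds for five descriptive rates: explicitly for the three hypoglycaemia rates, and by inference from Table 16.13 for overall AEs and SAEs. What needs no assumed event rate is the distorted weighting, about 10 to 11.5 times for an event in a participant followed for 4 weeks, and a median of 0 when under half the arm has an event. The loss of precision remains under constant risk, though its size depends on assumed leaving times. Upward bias is conditional. It ranges from 7% to 32% when assumed early risk is 3 to 5 times the later risk and 10% to 25% leave before week 52. It is nil under constant risk with leaving unrelated to events, or with no leavers. The primary analysis and the planned rate ratios in Table 16.15 are not affected. The change is worth making because it is cheap and brings Table 16.13 into line with the SAP's own section 6.

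**What to change.** In SAP 2.2.1 and Table 16.13, for overall AEs, overall SAEs and the ADA, Novo Nordisk and severe hypoglycaemia rates:

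- Replace the mean of individual rates with total events, total person-years and events per person-year by arm. Give a 95% CI that allows for repeat events in the same participant, for example from robust Poisson or negative binomial regression with log follow-up as offset.
- State the formula for the overall AE and SAE rates, which is now missing.
- Define total follow-up time as ending at study withdrawal or at the 52- or 104-week cut-off, whichever comes first.
- Remove the Baseline and Change columns for these rows, since an on-study event rate has no baseline value.

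The cost is a small amount of extra analysis and a revised table shell, with no new data. The SAP deliberately limits model fitting. The pooled rate is the essential part; the model is needed only for the interval.
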